# 8.2 Tissue Samples

Paired tumour biopsies will be collected pre-study (diagnostic biopsy) and at the end of Cycle 2, whenever possible. At the end of Cycle 2, half the sample will be placed in RNALater for storage at -80°C. Half will be fixed in 10% formalin and embedded in paraffin. Immunohistochemistry will be used to measure pERK, down-stream targets of ERK signalling and key substrates in the JNK, p38 MAPK and PI-3K/Akt pathways.

Immunohistochemistry will also assess the expression of angiogenic factors and activated caspase 3 with TUNEL as a marker for apoptosis. Changes in pERK and key members of other cell signalling pathways identified in the sub-study of PBMCs will be assessed by Western blot using protein lysates formed by homogenization of frozen tissue biopsy sections.

# 8.3 Blood samples

# 8.3.1 Angiogenic growth factors

Serum will be collected to measure changes in pro-angiogenic growth factors including angiopoietin-(Ang)-2, vascular endothelial growth factor-(VEGF)-A and VEGF-C using commercially available Enzyme-linked immunosorbent assay (ELISA) kits. Interleukin (IL)-6, and other key cytokines identified in the sub-study below of PBMCs will also be measured by ELISA.

- Blood samples will be collected at Cycle 1 Day 1 Pre-treatment, Cycle 1 Day 22/Cycle 2 Day 1, Cycle 2 Day 22/Cycle 3 Day 1, Cycle 4 Day 22/Cycle 5 Day 1 and Cycle 6 Day 22 (all +/- 1 day, except Cycle 1 Day 1 Pre-treatment).
- 8.5mls of blood should be collected in a BD vacutainer no-additive serum tube.
- Samples should be kept at room temperature for 30 minutes before centrifugation to ensure complete clotting.
- Samples should then be centrifuged at 2000g for 20minutes at room temperature.
- Supernatant should be decanted into a new tube and transferred into 5 x 200µl in 0.5ml eppendorf tubes and any remaining serum aliquoted into 1.5ml eppendorf tubes.
- All tubes should be individually labelled and logged with the patient's study number and treatment cycle.
- Samples should be transferred to a -80°C freezer for storage as soon as possible.
- Samples should be transferred to the central laboratory (University of Sheffield) on dry ice (see Laboratory Manual for courier details).

#### 8.3.2 Pharmacokinetics

Pharmacokinetic studies will be performed in phase I only.

The objectives are:

To describe the pharmacokinetics of selumetinib in combination with HAART. Non compartmental analysis will estimate Cmax, AUC0-24, clearance and t1/2 from peripheral blood measurements of both AZD6244 and its metabolites pre-dose, and at 2 and 6 hours post dose on day 1 and pre-dose day 15. Laboratory bioanalysis will be performed by Quotient BioResearch.

Peripheral blood will be sent to Lab21 for anti-retroviral drug levels on Cycle 1 Day 1 Pretreatment, Cycle 1 Day 15 and Cycle 4 Day 22/Cycle 5 Day 1.

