# 2.1.2 Secondary Objectives

- To describe the pharmacokinetics of selumetinib in combination with HAART, including the effects of selumetinib on HAART metabolism.
- To assess the toxicity of selumetinib in combination with HAART.
- To describe the pharmacodynamic effects of selumetinib in combination with HAART.
- Progression free survival rate at 6 months from commencing treatment.

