#### 2.2 Outcome Measures

### 2.2.1 Phase I

- Selumetinib and metabolite serum levels pre-dose and at 2 and 6 hours on day 1 and pre-dose on day 15.
- HAART drug levels pre-dose on days 1, 15 and at 12 weeks.

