# 7 TREATMENT DETAILS

# 7.1 Selumetinib

The Investigational Medicinal Product in this trial is selumetinib. The starting dose of selumetinib for each patient will be released with their Registration Number. Selumetinib should be taken twice daily approximately 12 hours apart with water, at least 2 hours after a meal and 1 hour before the next meal. Selumetinib capsules will be administered in doses as described in section 3 in a continuous 21 day cycle, unless disease progression (see section 7.4) or unacceptable toxicity is encountered. The trial design, dose levels and numbers of required patients are shown in section 3.1.

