#### Selumetinib drug levels

- Samples to be collected Cycle 1 Day 1 Pre-treatment, 2 hours and 6 hours post dose (after first set of tablets) pre-dose Cycle 1 Day 15.
- 5mls of venous blood should be collected into a K2-EDTA BD vacutainer
- Samples should be inverted several times to ensure adequate mixing.
- Samples should be centrifuged at 2000g for 20minutes at room temperature.
- 2x 500µl of plasma should be aliquoted to **polypropylene** eppendorf tubes.
- Tubes should be individually labeled with the patient's study number and sample time-point.
- Samples should be stored at -20°C.
- 1 x sample to be transferred on dry ice to Quotient Bioresearch for bioanalysis (all four sample time-points day 1 pre-dose, and at 2 and 6 hours post dose and pre-dose day 15 can be shipped together please refer to the Laboratory Manual for courier details).
- 1 x sample to be stored at the study centre as back-up.

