# 13.2 Statistical Analysis

#### 13.2.1 Phase I

Phase I consists of a dose finding study in the classic 3 + 3 design with fixed dose increments. Phase I data from monotherapy studies of selumetinib enable an initial dose estimate close to the MTD. The expected number of patients recruited to phase I is 12.

- A descriptive analysis will be undertaken to describe toxicity per cycle and dose intensity.
- Non compartmental analysis will estimate Cmax, AUC0-24, clearance and t1/2 from peripheral blood measurements of both AZD6244 and its metabolites.
- Percentage changes in anti-retroviral drug levels will be calculated.
- Percentage inhibition of pERK in tumour tissue will be calculated and correlated with tumour response. Changes to downstream proteins, apoptotic pathways and adaptive changes to other MAPK pathways will be assessed.
- Percentage changes in serum angiogenic markers will be calculated and correlated with tumour response.
- Percentage changes in HIV-viral load and CD4 count will be calculated.
- Response rate will be estimated with 90% confidence intervals.

 Number of treatment cycles completed, duration of response and progression free survival at 6 months from commencing treatment will be reported.

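### Non-compartmental AUC0-24, clearance and half-life of selumetinib are promised from samples that stop 6 hours after the first dose and cannot support them

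*Protocol*

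**What the plan says.** Section 8.3.2 states: "Non compartmental analysis will estimate C max , AUC 0-24 , clearance and t 1/2 from peripheral blood measurements of both AZD6244 and its metabolites". The statistical section, 13.2.1, repeats the method and the parameters ("Non compartmental analysis will estimate", then the same list).

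The samples are described in three places that agree:

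- 2.2.1, outcome measure: "Selumetinib and metabolite serum levels pre-dose and at 2 and 6 hours on day 1 and pre-dose on day 15".
- 8.3.2, analysis text: "pre-dose, and at 2 and 6 hours post dose on day 1 and pre-dose day 15".
- 8.3.2, sample handling, which also gives the count: "all four sample time-points day 1 pre-dose, and at 2 and 6 hours post dose and pre-dose day 15".

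On dosing, 7.1 says: "Selumetinib should be taken twice daily approximately 12 hours apart with water". Section 8.3.2 limits pharmacokinetic sampling to phase I, and 3.1.2 records that phase I is complete. No compartmental, population or sparse-sampling method is named.

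The secondary objective in 2.1.2 is wider: "To describe the pharmacokinetics of selumetinib in combination with HAART, including the effects of selumetinib on HAART metabolism".

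**The concern.** The protocol fixes a method, a list of parameters and a sampling schedule, and three of the four parameters do not follow from the schedule. Non-compartmental analysis uses the observed curve plus a short extrapolated tail. Here the observed part ends at 6 hours, halfway through the first dosing interval, and the rest would have to come from a slope drawn through two points.

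The stake is the phase I report. AUC0-24, clearance and half-life would appear there as estimates, for parent and metabolites, when they depend largely on extrapolation that cannot be checked. Every patient is already on HAART, so the trial has no selumetinib profile without HAART. A reader who wanted one would have to look outside the trial, and would take these numbers there.

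**Working it through.** The protocol gives no precision or sample-size figure for the pharmacokinetic analysis, so there is no stated number to reproduce. Steps 1 to 4 use only the protocol. Step 5 uses assumptions.

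**1. AUC0-24.** Samples per patient: 0, 2 and 6 h on day 1, and one pre-dose sample on day 15. Two of the four follow a dose within a profile.

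- Time covered on day 1: 6/24 = 25%, leaving 18 h unobserved.
- First dosing interval: 6/12 = 50% covered. Second interval: 0/12.

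These are shares of time. The share of area depends on kinetics that the protocol does not give. The de-escalation level in 3.1 is once daily; at that level there is no second dose, but the 18 unobserved hours remain.

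**2. Half-life.** With two points, λ = ln(C2/C6)/4 and t½ = 4 × ln 2 / ln(C2/C6) = 2.77 / ln(C2/C6). Two points fit an intercept and a slope, so the residual degrees of freedom are 2 − 2 = 0. Nothing can show whether the 2 h value already lies on the elimination phase. If C6 is not below C2, there is no estimate.

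**3. Clearance.** There are two routes to apparent oral clearance (CL/F).

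- Dose / AUC0-∞, with AUC0-∞ = AUC0-6 + C6/λ. This takes λ from step 2.
- Dose / AUC over one interval at steady state. Day 15 has one trough and no post-dose sample.

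**4. Day 15 trough as a substitute 12 h point.** It follows two weeks of dosing. Accumulation under 12-hourly dosing is 1/(1 − 2^(−12/t½)): 1/(1 − 1/16) = 1.07 at a half-life of 3 h and 1/(1 − 1/2) = 2.0 at 12 h. It is not a point on the day 1 curve.

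**5. Size of error, under assumptions not in the protocol.** One-compartment oral model; half-life 3 to 12 h; absorption rate 0.7 to 3 per h; two doses 12 h apart.

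Worked case, true half-life 5 h, absorption rate 0.7 per h: k = 0.693/5 = 0.1386. Concentration is proportional to e^(−kt) − e^(−0.7t), which is 0.758 − 0.247 = 0.511 at 2 h and 0.435 − 0.015 = 0.420 at 6 h. ln(0.511/0.420) = 0.196, so the two-point half-life is 2.77/0.196 = 14.1 h.

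Two-point half-life (h), without measurement error:

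| True half-life | Absorption 0.7/h | 1.5/h | 3/h |
|---|---|---|---|
| 3 h | 5.7 | 3.3 | 3.0 |
| 5 h | 14.1 | 5.7 | 5.0 |
| 8 h | 110.8 | 9.7 | 8.1 |
| 12 h | none | 16.0 | 12.1 |

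- With biexponential decline instead (distribution half-life 1.2 h), a true terminal half-life of 8 h is estimated as 2.4 to 4.3 h.
- Measurement error: a 15% CV gives a log-scale SD of 0.149, so the SD of the slope is 0.149 × √2/4 = 0.0527. At a true 5 h, the 5th to 95th percentile of the slope is 0.1386 ± 1.645 × 0.0527 = 0.0519 to 0.2253, a half-life of 13.4 down to 3.1 h. At a true 8 h (slope 0.0866), 0.0866/0.0527 = 1.64, so about 5% of patients show no decline.
- Share of true day 1 AUC0-24 that lies within 0-6 h: 20% to 38%.
- Extrapolated share of AUC0-∞: 32% to 97% where it can be computed (11 of the 12 cells). Estimated CL/F is then 0.11 to 1.19 times the true value.

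**The case against.** The best defence is that the pharmacokinetic aim is modest. The objective in 2.1.2 is descriptive, and the outcome measure in 2.2.1 is concentrations at exactly the sampled times. Both can be met. This stands, so a reader who infers that the pharmacokinetic objective as a whole must fail goes too far. Only the parameter list in 8.3.2 and 13.2.1 fails.

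Other stronger readings also lack support:

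- **Cmax.** The highest observed concentration is the usual non-compartmental Cmax. Under the assumptions above, the larger of the 2 h and 6 h values is 84% to 100% of the true peak. It needs a caveat, not deletion.
- **Dose escalation.** Section 3.1 makes dose level 3 depend partly on serum levels, which are measured. It does not mention AUC, clearance or half-life, and phase I is complete. The documents do not show that any dose decision rested on the unsupported parameters.
- **Comparison with monotherapy.** Section 1.3 discusses monotherapy Cmax and AUC0-24, but as ratios between formulations, and no comparison with this trial is planned.
- **One quarter of the AUC.** The 25% is time. The area share is 20% to 38%, and only under assumed kinetics.

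It is also fair to say that the largest errors in the table come from assumed slow absorption; with fast absorption and no measurement error, the two-point half-life is close. But the samples cannot tell a patient in the left column from one in the right. Nor can an analysis plan outside the protocol repair this: the protocol names both method and parameters, and no plan can supply missing samples.

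**Conclusion.** The point holds for AUC0-24, clearance and half-life, for parent and metabolites. That conclusion rests on the schedule alone: no concentration between 6 h and day 15, an unsampled second dose, a two-point slope with no residual degrees of freedom, and no profile at steady state. The error sizes in step 5 show plausible consequences and depend on the assumed kinetics. The consequence is limited: a secondary, descriptive, phase I analysis in an expected 12 patients, with neither primary objective affected. It is still worth correcting, because following the text as written would put unreliable numbers in the report.

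**What to change.** In 8.3.2 and 13.2.1, remove AUC0-24, clearance and half-life from the non-compartmental analysis. Report instead, for parent and metabolites and by dose level:

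- the concentrations at 2 h and 6 h on day 1;
- AUC0-6h by the trapezoidal rule, with the rule named. It is itself coarse: with a linear rise to 2 h and a logarithmic fall after it, it recovers 78% to 91% of the true 0-6 h area under the assumptions above;
- the day 15 trough;
- the highest observed concentration, labelled as the larger of the 2 h and 6 h values and as possibly below the true peak.

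Sections 2.1.2 and 2.2.1 can stay as they are. A model-based sparse-sampling analysis is optional; if one is wanted, the text should name its structure and the prior information it relies on.

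The change is to analysis wording only, with no new samples or visits. The downside is that fewer parameters can be set beside published monotherapy values.

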#### Selumetinib drug levels

- Samples to be collected Cycle 1 Day 1 Pre-treatment, 2 hours and 6 hours post dose (after first set of tablets) pre-dose Cycle 1 Day 15.
- 5mls of venous blood should be collected into a K2-EDTA BD vacutainer
- Samples should be inverted several times to ensure adequate mixing.
- Samples should be centrifuged at 2000g for 20minutes at room temperature.
- 2x 500µl of plasma should be aliquoted to **polypropylene** eppendorf tubes.
- Tubes should be individually labeled with the patient's study number and sample time-point.
- Samples should be stored at -20°C.
- 1 x sample to be transferred on dry ice to Quotient Bioresearch for bioanalysis (all four sample time-points day 1 pre-dose, and at 2 and 6 hours post dose and pre-dose day 15 can be shipped together please refer to the Laboratory Manual for courier details).
- 1 x sample to be stored at the study centre as back-up.

#### Anti-retroviral drug levels

- Samples to be collected Cycle 1 Day 1 Pre-treatment and Cycle 1 Day 15 and Cycle 4 Day 22/Cycle 5 Day 1.
- 5mls of venous blood should be collected into a K2-EDTA BD vacutainer
- Samples should be inverted several times to ensure adequate mixing.
- Samples should be centrifuged at 2000g for 20 minutes at room temperature.
- 2x 1000 µl of plasma should be aliquoted to 1.5 ml plastic screw top tubes.
- Samples should be stored at -20°C (or below) for 24 hours before sending.
- Samples should be sent to Lab21 for bio-analysis (please refer to the Laboratory Manual for courier details.

# 8.3.3 PBMC Sub-study

A sub-study will be undertaken in selected centres in 12 patients in total. In this sub-study requiring viable PBMCs, 50 mls of venous blood will be collected in Lithium Heparin tubes at Cycle 1 Day 1 Pretreatment, Cycle 3 Day 22/Cycle 4 Day 1 and Cycle 6 Day 22 (all +/- 1 day except Cycle 1 Day 1 Pretreatment) and couriered to Sheffield for analysis (please refer to the Laboratory Manual for courier details). Viable PBMCs obtained by FicoII-Paque density centrifugation will be cultured in 24 well plates. Samples will be split and aliquots will be lysed to obtain protein for Western blotting to measure levels of pERK in relation to ERK and of phosphorylation of key substrates in the JNK, p38 MAPK and PI-3K/Akt pathways. Changes to down-stream targets of ERK signalling, including c-fos and c-myc will be assessed along with key apoptotic proteins such as Bad and BcI-2. An aliquot of PBMCs will be challenged with TLR4 and 9 agonists or left untreated and production of IL-1 $\beta$ , tumour necrosis factor-(TNF)- $\alpha$ , IL-6, IL-10, IL-12 and type 1 interferons will be measured by cytometric bead array of culture supernatants. Reactive oxygen species (ROS) production by PBMCs will be measured by flow cytometry

using dichlorofluorescein (DCF) and cell survival assessed by Annexin V-PE/TO-PRO3 staining and flow cytometry.

#### 9 ADVERSE EVENT REPORTING

The collection and reporting of Adverse Events (AEs) will be in accordance with the Medicines for Human Use Clinical Trials Regulations 2004 and its subsequent amendments. Definitions of different types of AE are listed in Appendix 3. The Investigator should assess the seriousness and causality (relatedness) of all AEs experienced by the patient (this should be documented in the source data) with reference to the Investigator Brochure.

# 9.1 Reporting Requirements

#### 9.1.1 Adverse Events

All medical occurrences which meet the definition of an AE (see Appendix 3 for definition) should be reported. Please note in Phase I this includes all abnormal laboratory findings. In Phase II abnormal laboratory findings need only be recorded if the local investigator deems the finding as clinically significant. A pre-existing condition (including abnormal laboratory finding which meet CTCAE criteria) must not be reported as an AE unless the condition worsens by at least one CTCAE grade during the trial. The condition, however, must be reported on the Screening Case Report Form.

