# 3.2 Phase II

Patients will be recruited in a single-arm study at the RPTD, in order to determine objective tumour response using AIDS Clinical Trials Group Oncology Committee (ACTG) criteria (see Appendix 1). Patients recruited to the RPTD during phase I will be included in the phase II study. KS will be evaluated using clinical photographs of target lesions and bi-dimensional measurements every 3 weeks and/or CT imaging of assessable disease sites every 6 weeks during treatment. As in phase I, patients who continue to respond to selumetinib following completion of 6 cycles of therapy will be offered the option of continuing selumetinib. Patients who have been shown to derive benefit from selumetinib and HAART combined therapy at one year should be continued on this regimen as long as there has been no disease progression and their risk: benefit analysis, in the opinion of the Chief Investigator and treating physician, favours the continuation of treatment and with approval from AstraZeneca. To continue treatment beyond 6 cycles sites should contact the SCART Trial Office as described in section 3.1. Patients' HAART regimen should not be changed for their first 3 months on the trial (i.e. until after the C4D22/C5D1 visit) unless clinically necessary. If deemed clinically necessary, sites should contact the SCART Trial office to facilitate discussion with the Chief Investigator and Clinical Co-Investigators.

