#### 13.2.2 Phase II

Phase II will investigate the efficacy of selumetinib in combination with HAART in patients with KS. Patients recruited to the recommended phase II dose in phase I will be included in phase II.

In order to keep the trial the trial size as small as possible a Simon two-stage design will be used for patient accrual.

Phase II will accrue up to a total of 25 response evaluable patients (including those from phase I). The primary outcome measure of phase II is best objective tumour response up to the end of the 6th cycle. Objective tumour response is as defined by the ACTG criteria (refer to appendix 1 for details). Both CR and PR will count as responses for the purpose of the primary outcome.

- Response rate will be estimated with 90% confidence intervals.
- Toxicity per cycle and dose intensity will be reported.
- Number of treatment cycles completed, duration of response and progression free survival at 6 months from commencing treatment will be reported
- Percentage inhibition of pERK in tumour tissue will be calculated and correlated with tumour response. Changes to downstream proteins, apoptotic pathways and adaptive changes to other MAPK pathways will be assessed.
- Percentage changes in serum angiogenic markers will be calculated and correlated with tumour response.
- Percentage changes in HIV-viral load and CD4 count will be calculated.

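### Laboratory adverse events follow different recording rules in phases I and II, yet recommended-dose patients from both form one set for toxicity reporting: a minor point with an inexpensive repair

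*Protocol*

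**What the plan says.** Protocol section 9.1.1 asks sites to report every occurrence that meets the adverse event definition, then splits the laboratory rule by phase. For phase I: "Please note in Phase I this includes all abnormal laboratory findings". For phase II: "In Phase II abnormal laboratory findings need only be recorded if the local investigator deems the finding as clinically significant". One limit applies to both phases: "A pre-existing condition (including abnormal laboratory finding which meet CTCAE criteria) must not be reported as an AE unless the condition worsens", the threshold being at least one CTCAE grade. So phase I forms hold new or worsened abnormalities, not every abnormal value.

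Section 3.2 carries patients across: "Patients recruited to the RPTD during phase I will be included in the phase II study". Section 13.2.2 repeats it: "Patients recruited to the recommended phase II dose in phase I will be included in phase II". It also counts them within the phase II total of 25 response-evaluable patients.

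For that set, section 13.2.2 states: "Toxicity per cycle and dose intensity will be reported". It gives no split by phase of recruitment and does not say whether laboratory toxicity comes from adverse event forms or laboratory values. Section 2.1.2 makes toxicity a secondary objective: "To assess the toxicity of selumetinib in combination with HAART".

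Two further passages bear on the point. Section 7.9.8 has toxicity assessed every 21 days, and weekly during cycle 1 in phase I only. Sections 7.9.2.2 and 10.1 show haematology and biochemistry measured each cycle in phase II and entered on the Treatment Cycle Forms.

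**The concern.** Within the recommended-dose set, the same raised transaminase can be an adverse event in one patient and go unrecorded in another, depending only on the phase of entry. A laboratory rate counted from the forms then estimates neither the incidence of laboratory abnormalities nor the incidence of clinically significant ones. It also depends on how many patients happened to come from phase I.

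What is at stake is descriptive. Section 1.5.2 says the trial is to inform a later randomised study, and a reader of its toxicity table would want to know what a laboratory rate means. Several listed selumetinib effects are laboratory findings. In the section 7.3.1 table of commonly reported events, 7 of the 21 terms are laboratory ones (AST, ALT, ALP, albumin, anaemia, platelets, magnesium), all in the 10-20% column. The same section also lists raised creatine phosphokinase and phosphate as expected.

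**Working it through.** **Inputs**

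- Pooled denominator: 25 (sections 13.1.2 and 13.2.2).
- k, phase I patients carried over: not stated. The dose table in 3.1 gives a minimum of 3 per level, and the MTD definition in 3.1.2 refers to 6. I use 3 to 6, that is 3/25 = 12% to 6/25 = 24% of the set.
- T, proportion of patients with a new or worsened laboratory abnormality: not stated for this trial. Section 7.3.1 puts individual laboratory terms at 10-20% as reported events in other selumetinib studies. I take 15% for one term, and 40% or 60% as illustrations for any laboratory abnormality. All are assumptions.
- s, share judged clinically significant: not in the document. Assumed one third for the main example, and 0.25 to 0.75 as a range.

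**The plan's own figure.** Section 13.1.2 gives a Simon minimax design: 16 patients, stop at 1 or fewer responses, otherwise 25 in total, active at 5 or more. With response rates of 10% and 30%, exact two-stage binomial sums give a type I error of 0.0951, power of 0.9030 and a probability of 0.515 of stopping early under the null. A search confirms 25 as the minimax size for the stated 0.10 and 0.90. The denominator stands, and nothing below touches the response test.

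**Formulas**

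- Complete rule for all: T
- Phase II rule for all: T × s
- Pooled as recorded: [k × T + (25 − k) × T × s] / 25
- Effect of pooling (pooled minus phase II rule): (k/25) × T × (1 − s)
- Shortfall from complete recording: ((25 − k)/25) × T × (1 − s)

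**Main example**, T = 15%, s = 1/3:

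- k = 6: (6 × 0.15 + 19 × 0.05)/25 = 1.85/25 = 7.4%
- k = 3: (3 × 0.15 + 22 × 0.05)/25 = 1.55/25 = 6.2%
- Phase II rule for all: 5%. Complete rule for all: 15%.

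Pooling therefore adds 1.2 to 2.4 points. Across T = 10% to 20% with the same s, it adds from 0.12 × 0.10 × 2/3 = 0.8 points to 0.24 × 0.20 × 2/3 = 3.2 points.

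**Wider range**

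| T | s | Phase II rule | Pooled, k = 3 | Pooled, k = 6 | Complete rule |
|---|---|---|---|---|---|
| 40% | 0.25 | 10% | 13.6% | 17.2% | 40% |
| 40% | 0.50 | 20% | 22.4% | 24.8% | 40% |
| 40% | 0.75 | 30% | 31.2% | 32.4% | 40% |
| 60% | 0.25 | 15% | 20.4% | 25.8% | 60% |
| 60% | 0.50 | 30% | 33.6% | 37.2% | 60% |
| 60% | 0.75 | 45% | 46.8% | 48.6% | 60% |

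In these rows the pooled rate is 1.2 to 10.8 points above the phase II rule and 7.6 to 39.6 points below complete recording.

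**Splitting the gap.** The two rules differ by T × (1 − s). Pooling closes k/25 of that difference, 12% to 24%, whatever T and s are. The remaining 76% to 88% is the phase II rule. If non-evaluable patients are replaced (7.12) but stay in the toxicity table, the carried-over share is smaller still.

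**The case against.** The strongest reply is that the protocol does not commit itself to a pooled rate from adverse event forms. Section 13.2.2 says only that toxicity will be reported, sections 2.2.2 and 7.9.8 define toxicity by CTCAE grading, and the values are collected. A statistical analysis plan, not shown here, may grade from values or split by phase. A lighter laboratory rule in phase II is also not an error in itself. All of this stands. It makes the point conditional and small, and it means the data for a repair should exist. What it does not remove is that the protocol itself sets unequal recording rules and merges the patients. No later document can restore form entries that sites were told they need not make.

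Discretion also bites mainly on low grades. Under 7.4, treatment-related events of grade 3 or above are reported within 24 hours, and 7.4.2 ties treatment interruption to most grade 2 non-haematologic events, biochemistry included. An abnormality that interrupts treatment is unlikely to be called insignificant. That is an inference, but a reasonable one.

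A reader might infer that pooling conceals most laboratory toxicity, for example 37.2% shown against 60%. The document does not support that reading: with T = 60%, s = 0.5 and k = 6, the phase II rule alone gives 30%, so pooling moves the figure 7.2 points towards complete recording. A reader might also infer that selumetinib's known effects are mostly laboratory ones. In 7.3.1 all five events above 30% are clinical, and rash, fatigue and diarrhoea lead at grade 3 or above.

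**Conclusion.** The point holds as a minor one. If laboratory toxicity for the recommended-dose set is counted from adverse event forms, it mixes two ascertainment rules and equals neither single-rule rate unless every abnormality is judged significant. Relative to complete recording it under-counts, mainly at lower grades, and chiefly because of the phase II rule. Pooling contributes about 1 to 3 points for a single laboratory term at the 10-20% incidences of 7.3.1, and up to 10.8 points in the illustrations for any laboratory abnormality.

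These sizes rest on assumed values of T and s and on 3 to 6 carried-over patients. The mixing of rules does not. Clinical adverse events, serious adverse events, dose-limiting toxicity decisions and the objective response endpoint are unaffected.

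**What to change.** In section 13.2.2, state that laboratory toxicity for all patients treated at the recommended dose, from either phase, is derived by CTCAE v4.0 grading of the haematology and biochemistry values on the case report form. Report worst grade per patient and per cycle, relative to baseline. Use visits common to both phases, and flag or exclude any extra weekly cycle 1 values from phase I. Report investigator-recorded laboratory adverse events separately, by phase of recruitment. The phase II recording rule in 9.1.1 can stay as it is.

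The cost is a little programming, with no new visits or samples. The limit is that only collected analytes can be graded. Magnesium, for example, appears in the 7.3.1 table but is not named in the biochemistry panel of 7.9.2.2.
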